23.3 PROTOCOL AMENDMENT #1

- **General Purpose**

The purpose for this amendment is to:

- 1) Decrease age limit to ≥ 13 years to include adolescents as it was determined that the Q-Fix™ anchor is being used by sites in adolescents; it is important to obtain information on the safety and performance in the adolescent population as well as in adults. A secondary objective is added so that an analysis may be done on adolescents and young adults ages 13-21 years of age. As this retrospective study is granted a waiver of informed consent for adults, it is requested for adolescents as well.
- 2) Increase enrollment maximum to 450 subjects to allow for the enrollment of adolescents and additional Q-Fix™ MINI subjects (150 maximum per joint type.)
- 3) Revise the timeline to account for the enrollment of adolescents; this amendment is not expected to affect the overall study duration.
- 4) Include both open and arthroscopic surgeries in the study as it was determined that sites used the Q-Fix™ anchor in both arthroscopic and open soft tissue repair surgeries; it is important to obtain safety and performance data for both types of surgery. Also clarified that as the study is collecting real world safety data, use in knee, shoulder, and hip may be collected beyond the indications for use.
- 5) Clarify that another enrollment date may be used if agreed upon by Investigators and site, as long as a bias is not introduced using this date. In addition, the enrollment start date for Q-Fix™ MINI may be different than the start date for the 1.8 and 2.8mm Q-Fix™ anchors to ensure that the data is collected on all 3 sizes of the Q-Fix™ anchor.

- **Rationale**

The rationale for the changes is as follows:

- 1) From the screening and enrollment logs provided by the sites to the Sponsor, individuals <18 years old are receiving Q-Fix™ anchors, but this population is not included per the current

CONFIDENTIAL AND PROPRIETARY

This document contains information that is confidential and proprietary to Smith & Nephew PLC and Smith & Nephew, Inc. and is intended for use only by Smith & Nephew and its manufacturer. It shall not be reproduced or copied in whole or in part, nor shall the contents be disclosed by any means without prior written permission from Smith & Nephew, nor shall anyone make any use of it that is contrary to the expressed or implied wishes of Smith & Nephew.

Study Protocol—Device	
Safety and Performance of Q-Fix™ All-Suture Anchor System	Number: 17-5010-11
	Version: 2.0 05SEP2019
	Page: Page 55 of 62

eligibility criteria. A goal of this post-market study is to determine the safety and performance of the Q-Fix™ anchor in populations that are receiving the Q-Fix™ anchor, so by not including adolescents, this study is unable to analyze whether the anchor is safe and performs well in a population that physicians are already using the Q-Fix™ anchor in: individuals aged 13 to 17 years old. A secondary exploratory analysis will be conducted on adolescents and young adults ages 13-21 years of age. Given that the current processes for this retrospective study will not change, it is requested that a waiver of consent be extended to include the adolescent population as well the adult population.

- 2) In order to enroll adolescents, as well as Q-Fix™ MINI anchors, the study maximum is increased from 360 to 450 subjects (150 subjects per indication). As the sites will be enrolling subjects that were originally excluded, this number is enough to include all adolescents that were previously excluded per the site Screening Logs.
- 3) In order to enroll adolescents, data collection is increased from 12 to 16 months. Follow-up is expected to take shorter than originally planned; therefore, the overall timeline for the study remains at 2.5 years.
- 4) Physicians are already using the Q-Fix™ anchor in both open and arthroscopic surgeries. In order to adequately describe the safety and performance of the Q-Fix™ anchor post-market, it is important to include both surgery types. A protocol waiver to include these individuals was already granted by all IRBs; therefore, the protocol is being revised to capture this information, as well as clarifying that the Q-Fix™ is indicated for use in soft tissue repair (not just instability). Additionally, clarified that as the study is collecting retrospective real world safety and performance data, sites may provide data on use in the shoulder, knee, or hip that is not listed in the indications for use.
- 5) The wording on the statement for enrolling subjects is not clear and there has been confusion in interpreting this line by the sites: “To eliminate the potential for bias, Investigators will consecutively screen subjects by date of surgery, starting with subjects that have undergone arthroscopic tissue repair with Q-Fix™ All-Suture Anchor system in the past 12 months as of the

CONFIDENTIAL AND PROPRIETARY

This document contains information that is confidential and proprietary to Smith & Nephew PLC and Smith & Nephew, Inc. and is intended for use only by Smith & Nephew and its manufacturer. It shall not be reproduced or copied in whole or in part, nor shall the contents be disclosed by any means without prior written permission from Smith & Nephew, nor shall anyone make any use of it that is contrary to the expressed or implied wishes of Smith & Nephew.

Study Protocol—Device	
Safety and Performance of Q-Fix™ All-Suture Anchor System	Number: 17-5010-11
	Version: 2.0 05SEP2019
	Page: Page 56 of 62

IRB approval date.” Biostatisticians confirmed that the goal of that statement was to ensure that sites were not selecting records to prevent bias, and therefore this was broadened to include that a start date may be agreed upon by the Site and Sponsor. In addition, as the Q-Fix™ MINI anchor was released later than the 1.8mm and 2.8mm Q-Fix™ anchors, to ensure enrollment of MINI anchors, a more recent date will need to be used by the sites to specifically target Q-Fix™ MINI subjects.

- **Effect on Study Status**

These changes does not affect subjects that are already enrolled and does not affect the Case Report Forms. Current enrollment is 106 hip subjects, 99 shoulder subjects, and 24 knee subjects across all 5 sites that are participating in the study. If approval is received to enroll adolescents, the Statistical Analysis Plan will be revised to include adolescents to reflect the change in Secondary Endpoints. This change is not expected to affect the overall timeline of 2.5 years, however, enrollment is expected to require 16 months rather than 12 months and follow-up was decreased from 6 months to 2 months.

CONFIDENTIAL AND PROPRIETARY

This document contains information that is confidential and proprietary to Smith & Nephew PLC and Smith & Nephew, Inc. and is intended for use only by Smith & Nephew and its manufacturer. It shall not be reproduced or copied in whole or in part, nor shall the contents be disclosed by any means without prior written permission from Smith & Nephew, nor shall anyone make any use of it that is contrary to the expressed or implied wishes of Smith & Nephew.

Study Protocol—Device	
Safety and Performance of Q-Fix™ All-Suture Anchor System	Number: 17-5010-11
	Version: 2.0 05SEP2019
	Page: Page 57 of 62

■ **Details**

Section	Current Text 26JUN2018 Version 1.0	Revised Text 05SEP2019 Version 2.0

Head of Global Clinical Strategy	[name], Clinical Strategy Lead						
Head of Global Biostatistics	[name], Head of Global Biostatistics						
Medical Affairs Representative	[name], Medical Affairs Representative						
2. Synopsis Sample Size	
A total minimum sample size of 90 subjects is proposed with a maximum of 360 subjects (depending on market share) for approved joint indications.
 
Maximum 120
	
A total minimum sample size of 90 subjects is proposed with a maximum of 450 subjects (depending on market share) for approved joint indications.
 
Maximum 150
					
2. Synopsis Inclusion Criteria	
1. Subject has undergone arthroscopic instability repair with Q-Fix™ All-Suture Anchor System
	
1. Subject has undergone arthroscopic or open soft tissue repair with Q-Fix™ All-Suture Anchor System
 
2. Subject was ≥ 13 of age at time of
					

CONFIDENTIAL AND PROPRIETARY

This document contains information that is confidential and proprietary to Smith & Nephew PLC and Smith & Nephew, Inc. and is intended for use only by Smith & Nephew and its manufacturer. It shall not be reproduced or copied in whole or in part, nor shall the contents be disclosed by any means without prior written permission from Smith & Nephew, nor shall anyone make any use of it that is contrary to the expressed or implied wishes of Smith & Nephew.

Study Protocol—Device	
Safety and Performance of Q-Fix™ All-Suture Anchor System	Number: 17-5010-11
	Version: 2.0 05SEP2019
	Page: Page 59 of 62

	2. Subject was ≥ 18 of age at time of surgery	surgery
2. Synopsis Study Duration	12 months for subject enrollment 6 months for follow-up	16 months for subject enrollment 2 months for follow-up
2. Synopsis Secondary Endpoints		Clinical success rate in adolescents and young adults, defined as subjects ages 13-21 years of age without re-intervention at 6 and 12 months post-operative
4. Table of Contents and throughout protocol	Original sections and page numbers	Updated sections and page numbers
5.1 Background	Non-absorbable, soft suture anchors have recently been introduced for use in arthroscopic soft tissue to bone reattachment. Suture anchors are continuously evolving to improve anchor strength and to facilitate arthroscopic procedures.	Non-absorbable, soft suture anchors have recently been introduced for use in arthroscopic or open soft tissue to bone reattachment. Suture anchors are continuously evolving to improve anchor strength and to facilitate arthroscopic or open procedures.
8.1.1 Indications	Note: Foot, ankle, elbow, hand and wrist indications are not included in	Note: Foot, ankle, elbow, hand and wrist indications are not included in the above list as data will not be collected. As the

CONFIDENTIAL AND PROPRIETARY

This document contains information that is confidential and proprietary to Smith & Nephew PLC and Smith & Nephew, Inc. and is intended for use only by Smith & Nephew and its manufacturer. It shall not be reproduced or copied in whole or in part, nor shall the contents be disclosed by any means without prior written permission from Smith & Nephew, nor shall anyone make any use of it that is contrary to the expressed or implied wishes of Smith & Nephew.

Study Protocol—Device	
Safety and Performance of Q-Fix™ All-Suture Anchor System	Number: 17-5010-11
	Version: 2.0 05SEP2019
	Page: Page 60 of 62

	the above list as data will not be collected.	study is collecting real world data retrospectively, data may be collected on the shoulder, knee, or hip beyond the indications listed above.
9.1 Subject Population	To eliminate the potential for bias, Investigators will consecutively screen subjects by date of surgery, starting with subjects that have undergone arthroscopic instability repair with Q-Fix™ All-Suture Anchor system in the past 12 months as of the IRB approval date.	To eliminate the potential for bias, Investigators will consecutively screen subjects by date of surgery, starting with subjects that have undergone arthroscopic or open soft tissue repair with Q-Fix™ All-Suture Anchor system in the past 12 months as of the IRB approval date, or using another date as agreed upon by the Investigators and site. In addition, to ensure enrollment of Q-Fix MINI subjects, a different enrollment start date may be selected to enroll Q-Fix MINI subjects only.
9.2 Inclusion Criteria	
 1. Subject has undergone arthroscopic or open soft tissue repair with Q-Fix™ All-Suture Anchor System 2. Subject was ≥ 13 of age at time of surgery 	
 1. Subject has undergone arthroscopic or open soft tissue repair with Q-Fix™ All-Suture Anchor System 2. Subject was ≥ 13 of age at time of surgery
9.5 Informed Consent		If the subject is an adolescent ages 13-17 years old, a signed adolescent informed consent form will be required of the

CONFIDENTIAL AND PROPRIETARY

This document contains information that is confidential and proprietary to Smith & Nephew PLC and Smith & Nephew, Inc. and is intended for use only by Smith & Nephew and its manufacturer. It shall not be reproduced or copied in whole or in part, nor shall the contents be disclosed by any means without prior written permission from Smith & Nephew, nor shall anyone make any use of it that is contrary to the expressed or implied wishes of Smith & Nephew.

Study Protocol—Device	
Safety and Performance of Q-Fix™ All-Suture Anchor System	Number: 17-5010-11
	Version: 2.0 05SEP2019
	Page: Page 61 of 62

		subject as well as a signed parental informed consent form of a parent or guardian.
10.1 Study Design	A minimum of 90 subjects and a maximum of 360 subjects in the United States who underwent surgery in the knee, shoulder or hip using the Q-Fix™ All- Suture Anchor System are planned to be enrolled into the study after the fulfilment of all inclusion and exclusion criteria.	A minimum of 90 subjects and a maximum of 450 subjects in the United States who underwent surgery in the knee, shoulder or hip using the Q-Fix™ All- Suture Anchor System are planned to be enrolled into the study after the fulfilment of all inclusion and exclusion criteria.
10.2.2 Secondary Endpoints		Clinical success rate in adolescents and young adults, defined as subjects ages 13-21 years of age without re-intervention at 6 and 12 months post-operative
10.3.3 Balanced Covariates	The inclusion/exclusion criteria will be generalizable and applicable to the widest possible subset of the population suffering from arthroscopic instability.	The inclusion/exclusion criteria will be generalizable and applicable to the widest possible subset of the population requiring arthroscopic or open surgery for soft tissue repair.
12.2 Analysis Populations	Safety Population (SAF): This includes all subjects who enroll in the study who had previously undergone arthroscopic repair using the Q-Fix™	Safety Population (SAF): This includes all subjects who enroll in the study who had previously undergone arthroscopic or open soft tissue repair using the Q-Fix™

CONFIDENTIAL AND PROPRIETARY

This document contains information that is confidential and proprietary to Smith & Nephew PLC and Smith & Nephew, Inc. and is intended for use only by Smith & Nephew and its manufacturer. It shall not be reproduced or copied in whole or in part, nor shall the contents be disclosed by any means without prior written permission from Smith & Nephew, nor shall anyone make any use of it that is contrary to the expressed or implied wishes of Smith & Nephew.

Study Protocol—Device	
Safety and Performance of Q-Fix™ All-Suture Anchor System	Number: 17-5010-11
	Version: 2.0 05SEP2019
	Page: Page 62 of 62

	All-Suture Anchor System i.e. subjects who only provide retrospective data.	All-Suture Anchor System i.e. subjects who only provide retrospective data.
12.3.2 Analysis of Secondary Endpoint(s)		Clinical success rate on adolescents and young adults, defined as subjects ages 13-21 without re-intervention at 6 and 12 months post-operative, as assessed by the surgeon. The same type of analysis carried out on the primary endpoint would be implemented here as well.

CONFIDENTIAL AND PROPRIETARY

This document contains information that is confidential and proprietary to Smith & Nephew PLC and Smith & Nephew, Inc. and is intended for use only by Smith & Nephew and its manufacturer. It shall not be reproduced or copied in whole or in part, nor shall the contents be disclosed by any means without prior written permission from Smith & Nephew, nor shall anyone make any use of it that is contrary to the expressed or implied wishes of Smith & Nephew.

## 1. List of Abbreviations

Abbreviation	Definition
ADE	Adverse Device Effect(s)
AE	Adverse Event(s)
AEMB	Adverse Event Monitoring Board
CI	Confidence Interval
CRF	Case Report Form(s)
CSM	Clinical Study Manager
CSR	Clinical study Report
DevD	Device Deficiency(ies)
FU	Follow-Up
IBT	Iliotibial Band Syndrome
LCL	Lateral Collateral Ligament
LL	Lower Limit
MCL	Medial Collateral Ligament
MDD	Medical Device Directive
N (or n)	Total Sample Size (or subgroup sample size)
N/A	Not Applicable
NSAE	Non-Serious Adverse Event(s)
PRO	Patient Reported Outcome(s)
QoL	Quality of Life
ROM	Range of Motion
SADE	Serious Adverse Device Effect(s)
SAE	Serious Adverse Event(s)
SAP	Statistical Analysis Plan

### CONFIDENTIAL AND PROPRIETARY

This document contains information that is confidential and proprietary to Smith & Nephew PLC and Smith & Nephew, Inc. and is intended for use only by Smith & Nephew and its manufacturer. It shall not be reproduced or copied in whole or in part, nor shall the contents be disclosed by any means without prior written permission from Smith & Nephew, nor shall anyone make any use of it that is contrary to the expressed or implied wishes of Smith & Nephew.

Statistical Analysis Plan	
Safety and Performance of Q-Fix ® All-Suture Anchor System	Number: 17-5010-11
	Version: 2.0, 23-Oct-2019
	Page: 6 of 20

Abbreviation	Definition
SD	Standard Deviation
SLAP	Superior Labral Tear from Anterior to Posterior
TFL	Tables, Figures, and Listings
UADE	Unanticipated Adverse Device Effect(s)
VAS	Visual Analogue Scale
VMO	Vastus medialis obliquus

## 2. Introduction

Post-Market Clinical Follow-up is needed to address existing clinical data and gaps on the existing Q-FIX° device and meet existing MDD/MEDDEV requirements.

The purpose of this study to assess the safety and performance of the Q-Fix° All-Suture Anchor System. This Statistical Analysis Plan (SAP) is based on protocol number 17-5010-11 version 2.0, dated 05Sep2019. This SAP presents a detailed interpretation of the study protocol by describing the statistical analyses that will be carried out for the study in greater detail than specified in the protocol. Supporting documents used to create this SAP are the Study Protocol and the Case Report Forms (CRFs). Table, Figure, and Listing (TFL) shells will accompany the SAP.

## 3. Study Design

This is a retrospective, multi-center, case series to evaluate the 1-year safety and effectiveness of the Q-Fix° All-Suture Anchor System for arthroscopic repair when used for any of the following:

- **Shoulder:** Bankart lesion repair; superior labral tear from anterior to posterior( SLAP) lesion repair; acromio-clavicular repair; capsular shift/capsulolabral reconstruction; deltoid repair; rotator cuff repair; biceps tenodesis.
- **Hip:** Acetabular labral repair.
- **Knee:** Extra-capsular repair: medial collateral ligament (MCL), lateral collateral ligament (LCL) and posterior oblique ligament; Iliotibial band tenodesis (IBT); patellar tendon repair; vastus medialis obliquus advancement (VMO); joint capsule closure.

As the study is collecting real world data retrospectively, data may be collected on the shoulder, knee, or hip beyond the indications listed above.

Table 1 displays the information about the schedule of assessments for this study.

## Schedule of Assessments

**Table 1. Study Procedures by Visit**

Schedule of events	Chart Review 		
	Screening	182 days post-op (±91 Days)	365 days post-op (± 91 Days )
Inclusion/Exclusion	X		
Case History Review ***	X		
Implant Status 	X	X	X
VAS	X	X	X
ROM	X	X	X
Concomitant Medications, Procedures 	*	*	*
AE Assessment	*	*	*
Serious Adverse Event (SAE) / Adverse Device Effect (ADE) / Device Deficiency (DevD)	*	*	*
End of Study/Subject disposition	*	*	*

Given the retrospective study design, data will be collected to the extent it is available.

Informed consent/waiver of informed consent from the IRB/EC must be obtained prior to retrospective data collection.

Subjects who have undergone a revision procedure of the anchor will be considered terminated from the study from the date of the revision. Study related data will not be collected following the date of the revision.

 Any concomitant medications/ procedures associated with an AE, SAE or SADE will be recorded.

\*if applicable

\*\*\* Review of subject demographics, medical history, operative, post-op, discharge, and cumulative AE's occurring since date of surgery

#### 4. Study Objectives

##### 4.1 Primary Objective

The purpose of this study is to demonstrate the safety and performance of the Q-Fix® All-Suture Anchor System in hip, shoulder and knee repair.

#### 5. Study Endpoints

##### 5.1 Primary Endpoints

- Clinical success rate, defined as subjects without re-intervention at 6 months post- operative, as assessed by the surgeon

##### 5.2 Secondary Endpoints

- Clinical success rate, defined as subjects without re-intervention at 12 months post- operative, as assessed by the surgeon
- Visual Analog Scale-pain
- ROM
- Clinical success rate in adolescents and young adults, defined as subjects ages 13-21 years of age without re-intervention at 6 and 12 months post-operative

##### 5.3 Safety Endpoints

- Adverse events, to be evaluated by type, frequency, severity an relatedness to the study treatment
- Device-related re-intervention
- All adverse events (AEs) occurring from the time of surgery until revision or study completion
- Device related AE and SAE's

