9.3 EXCLUSION CRITERIA

Any one (1) of the following criteria will disqualify a potential subject from participation in the study:

1. Subject is ≤ 6 months post-operative
2. Subject is entered in another investigational drug, biologic, or device study or has been treated with an investigational product within 12 months post-operative.

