11. STUDY PROCEDURES

11.1 VISITS AND EXAMINATIONS

11.1.1 Summary

For a summary of the required procedures by visit, refer to Table 11.1-1: Study Procedures by Visit.

Table 11.1-1: Study Procedures by Visit

Schedule of Events	Chart Review ^{1,2}		
	Screening	182 days post-op 6M (±91 Days)	365 days post-op 12M (± 91 Days)
Inclusion/Exclusion	X		
Case History Review***	X		
Implant Status ³	X	X	X
VAS	X	X	X
ROM	X	X	X
Concomitant Medications, Procedures ⁴	*	*	*
AE Assessment	*	*	*
Study Implant Disposition	*	*	*
Serious Adverse Event (SAE) / Adverse Device Effect (ADE) / Device Deficiency (DevD) Assessment	*	*	*
End of Study/Subject disposition	*	*	*

¹ Given the retrospective study design, data will be collected to the extent it is available.

² Informed consent/waiver of informed consent from the IRB must be obtained prior to retrospective data collection.

CONFIDENTIAL AND PROPRIETARY

This document contains information that is confidential and proprietary to Smith & Nephew PLC and Smith & Nephew, Inc. and is intended for use only by Smith & Nephew and its manufacturer. It shall not be reproduced or copied in whole or in part, nor shall the contents be disclosed by any means without prior written permission from Smith & Nephew, nor shall anyone make any use of it that is contrary to the expressed or implied wishes of Smith & Nephew.

Study Protocol—Device	
Safety and Performance of Q-Fix™ All-Suture Anchor System	Number: 17-5010-11
	Version: 2.0 05SEP2019
	Page: Page 26 of 62

³ Subjects who have undergone a revision procedure of the anchor will be considered terminated from the study from the date of the revision. Study related data will not be collected following the date of the revision.

⁴ Any concomitant medications/ procedures associated with an AE, SAE or SADE will be recorded.

* If applicable

*** Review of subject demographics, medical history, operative, post-operative, discharge, and cumulative AE's occurring since date of surgery

CONFIDENTIAL AND PROPRIETARY

This document contains information that is confidential and proprietary to Smith & Nephew PLC and Smith & Nephew, Inc. and is intended for use only by Smith & Nephew and its manufacturer. It shall not be reproduced or copied in whole or in part, nor shall the contents be disclosed by any means without prior written permission from Smith & Nephew, nor shall anyone make any use of it that is contrary to the expressed or implied wishes of Smith & Nephew.

Study Protocol—Device	

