### Per Protocol Population

This includes all subjects in the Safety Population who meet the inclusion/exclusion criteria and who did not encounter major deviations leading to exclusion from study. Major protocol deviations leading to removal from the PP population will include but not restricted to the following: (1) termination from the study due to non-study related reasons such as subject lost to follow-up or death.

The final assignment of a subject to the per-protocol population will be established after a review of all protocol deviations have been evaluated and deviations that would warrant exclusion of a subject from the Safety population are identified. Subjects excluded from the per-protocol population will be documented together with their reason for exclusion.

Statistical analysis will be performed using each of the subject populations as follows: (1) Analysis of the primary and secondary endpoints will be performed separately using the Per Protocol Population. (2) All safety analyses will utilize the Safety Population. (3) The Safety Population will be additionally utilized for sensitivity analysis of the primary endpoint.

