#### 7.4.4 Derived Data for the Safety Endpoints

Time to Event will be defined as: Start Date – Operative Date

Duration = End Date - Start Date

Start Date for AE will be based on Original AE Report Date. For AEs where resolution has occurred:

End Date for AE will be based on the AE Stop Date or Death Date.

When there is a Follow-up AE, the end date will come from the AE Stop Date or Death Date on the latest or highest numbered Follow-up AE.

For the Serious AE listing,

Duration = End Date - Start Date

Start Date for SAE will be based on SAE Report Date. For SAEs where resolution has occurred:

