#### 7.9.4 Safety Analysis

The total number of AEs, and the total number of subjects experiencing an AE will be presented by Classification from the Investigator and the AEMB as per the tables below. 

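### The AE tables give crude percentages over unequal follow-up, so they do not estimate the 1-year safety that SAP section 3 says the study evaluates

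*SAP*

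**What the plan says.** SAP section 3 describes a retrospective, multi-center "case series to evaluate the 1-year safety and effectiveness" of the device. SAP 5.3 lists as a safety endpoint "All adverse events (AEs) occurring from the time of surgery until revision or study completion"; Protocol 10.2.3 has the same endpoint. Neither document gives study completion as a post-operative day.

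The planned AE summaries are in SAP 7.9.4. The number of events and "the total number of subjects experiencing an AE will be presented by Classification", and the table shells hold a count and a percentage. The denominator comes from SAP 7.2: "All safety analyses will utilize the Safety Population", which means everyone enrolled. SAP 7.3 plans no imputation.

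SAP 7.4.4 sets up a time variable ("Time to Event will be defined as" start date minus operative date), with the start date taken from the AE report. No analysis in SAP 7.9 uses it. The day-273 and day-456 cut-offs in SAP 7.4.1 and 7.4.2 apply to revisions only.

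**The concern.** A crude percentage estimates a 1-year risk only if nearly everyone is observed for a year and events after a year are left out. Neither condition is secured here.

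- Entry is open to anyone past the exclusion "Subject is ≤ 6 months post-operative" (Protocol 9.3), and the Protocol synopsis allows 2 months for follow-up.
- The last scheduled review is day 365 ± 91, which closes on day 456.
- Data collection stops at revision (footnote 3 of the schedule). Loss to follow-up is judged against each site's standard of care (Protocol 9.7), and lost subjects remain in the Safety Population.
- The screening chart review gathers "cumulative AE's occurring since date of surgery" (Protocol Table 11.1-1), with no upper day stated.

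The reported AE percentage would therefore reflect the enrolment calendar as well as the device. A reader who takes it as the 1-year safety result promised in section 3, or compares it with another anchor's 1-year figure, could be misled in either direction.

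**Working it through.** The documents state no AE risk and no AE precision, so there is no figure of the plan's own to reproduce. The sample-size figures concern clinical success and do not bear on this point.

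**Observation time per subject**
- Shortest without revision or loss: just over 6 months, about 183 days (Protocol 9.3).
- Entry just past 6 months plus the 2-month follow-up period (Protocol synopsis): about 8 months, or 244 days. This falls short of day 365 − 91 = 274, when the 12-month window opens.
- Longest on the schedule: 365 + 91 = day 456, about 15 months (SAP 7.4).
- Ratio of longest to shortest: 456 / 183 = 2.5.

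**Assumptions.** The 1-year risk R is not given. I take 10%, with a range of 5% to 20%. The risk by month t is F(t) = 1 − (1 − R)^((t/12)^k), where k = 1 is a constant hazard and k = 0.5 puts events early.

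**Common follow-up, R = 10%, k = 1**
- 183 days: 1 − 0.90^(183/365) = 5.1%
- 456 days: 1 − 0.90^(456/365) = 12.3%

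**Follow-up uniform over 6 to 15 months, R = 10%, k = 1**
- Mean of F = 1 − [0.90^(6/12) − 0.90^(15/12)] / [9 × (−ln 0.90)/12]
- = 1 − (0.9487 − 0.8766) / 0.0790 = 8.8%

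**Expected crude percentage, by scenario**

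| Follow-up | R = 5%, constant | R = 10%, constant | R = 20%, constant | R = 10%, early events |
|---|---|---|---|---|
| all 6 months | 2.5 | 5.1 | 10.6 | 7.2 |
| all 8 months | 3.4 | 6.8 | 13.8 | 8.2 |
| all 12 months | 5.0 | 10.0 | 20.0 | 10.0 |
| all 15 months | 6.2 | 12.3 | 24.3 | 11.1 |
| uniform 6 to 15 months | 4.4 | 8.8 | 17.6 | 9.3 |

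The rows with one common follow-up time bound the problem. The uniform row shows what a mixed cohort could look like. A cumulative incidence evaluated at 12 months targets R whatever the follow-up mix, provided censoring is not informative.

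**The case against.** Several points on the other side are fair.

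**A 2-year window is not supported.** A reader might infer that AEs accrue for two years or more, since the screening start date is flexible and the chart review has no stated upper day. The same 10% risk would then read as 1 − 0.90^(730/365) = 19.0%. The documents do not favour this reading. Protocol 14.3 and 14.3.1 treat completion as belonging to the individual subject, the schedule ends with the 12-month review, and Protocol 14 keeps device effects after study completion out of the database. What remains is that no AE text writes the cut-off down.

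**Nor is a particular direction.** A reader might infer that the crude figure must read low, especially for MINI subjects, who may have a later start date. Nothing shows that short follow-up dominates. Protocol 9.5 seeks the consent waiver for subjects who have had a 12-month visit, have died or are lost, and Protocol 9.8.1 asks for 12-month data on everyone. Follow-up by anchor size is not given.

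**The effect may be small.** In the mixed cohort the gap is about one percentage point on an assumed 10%. If events come early and most charts reach a year, little changes.

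**The 1-year horizon appears only in SAP section 3.** The objectives in Protocol 7.1 and SAP 4.1 set none, and no AE table is labelled as a 1-year risk. SAP 7.6 reports percentage follow-up by visit, which helps a reader judge exposure but does not correct the AE percentages. The separate table shells mentioned in SAP section 2 are not in the documents and might use the time variable.

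These points limit the size of the problem. They do not turn an untimed percentage into a 1-year estimate.

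**Conclusion.** The point holds in this form: as written, the AE percentages are crude proportions over unequal follow-up and do not estimate the 1-year safety named in SAP section 3. Under the assumed 10% risk and constant hazard, they would lie between 5.1% and 12.3% if everyone had the shortest or the longest scheduled follow-up, and near 8.8% to 9.3% for an even 6-to-15-month mix. The risk level, the hazard shape and the follow-up spread are all assumptions; the true size and direction cannot be determined from the documents.

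The primary endpoint and the 12-month re-intervention endpoint have their own day cut-offs and are outside this point. Device-related re-intervention, tabulated in SAP 7.9.2 with no time limit stated there, shares the gap. The change is worth making before database lock, but the study's main result does not hang on it.

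**What to change.** 1. **SAP 7.4.4:** define each subject's AE observation as running from surgery to the earliest of revision, withdrawal, death, last chart contact, or the end of the 12-month window (day 456). Base time to event on the AE onset date instead of the report date, which in a chart review can be much later.
2. **SAP 7.9.4:** add the cumulative incidence by day 365 of a first device- or procedure-related AE (Kaplan-Meier, 95% CI, numbers at risk) and events per 100 subject-years, with a summary of follow-up time. Keep the crude tables as support and state their denominator.
3. **Protocol 14 and 14.2:** reconcile which events are captured. Section 14 requires related events from surgery onward but all SAEs only after consent, a date that does not exist for subjects under a waiver; section 14.2 says AEs of any kind are recorded. Limit the time-based analysis to event types captured throughout.

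**Cost:** SAP wording and two extra tables. The documents do not show that onset and last-contact dates are on the CRF, so this must be confirmed or the dates taken from the charts. Censoring at last chart contact may be informative, for example if subjects without problems stop returning; the report should say so.
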